	Concordance of intrahepatic localization tessellation discrimination of Tc 99m sulfur colloid (intrahepatic disease heterogeneity) by SPECT/CT imaging and elastography	
Data Analyses	The following analysis population will be defined for the study:	
	• Intent-to-Diagnose (ITD) Population - Subjects who are enrolled in the study, administered Tc 99m tilmanocept and unfiltered Tc 99m sulfur colloid, and are imaged will be included in the ITD analysis population.	
	• Safety Population – All patients who are enrolled and administered Tc 99m tilmanocept and unfiltered Tc 99m sulfur colloid in the study will be included in the safety population.	
	All safety data analyses will be conducted on the safety population. All efficacy data analyses will be conducted on the ITD population.	
	The number and percentage of subjects experiencing noxious pharmacologic activity or ADRs will be tabulated by subject type, Tc 99m tilmanocept dose group (if applicable), and overall.	

Confidential Page 12 of 71

Tc 99m tilmanocept Clinical Study Protocol Number: NAV3-30

> Per subject localization rates and percentage will be calculated by time point, by subject type, Tc 99m tilmanocept dose group (if applicable), and overall.

> Localization intensities (tessellation) will be summarized by descriptive statistics (mean, median, standard deviation, minimum, maximum and range) at each time point. All results will be compared to statistics computed on the control group at each time point.

Confidential Page 13 of 71

Clinical Study Protocol Number: NAV3-30

LIST OF ABBREVIATIONS AND DEFINITIONS OF TERMS

ADR adverse drug reaction

AE adverse event

ALT alanine aminotransferase (SGPT)

AST aspartate aminotransferase (SGOT)

[figure not shown]
BMI body mass index

BUN blood urea nitrogen

CCL2 CC-chemokine ligand 2

CCR2 CC-chemokine receptor 2

CD206 Mannose-binding receptor (Ca2+-binding lectin)

CO₂ carbon dioxide

CRA clinical research associate

CRF case report form

CRO contract research organization

CSF1 Macrophage colony-stimulating factor 1

CSF1R CSF1 receptor

CT X-ray computed tomography

CX3CR1 CX3C-chemokine receptor 1

CXCL CXC-chemokine ligand

CXCR CXC-chemokine receptor

Clinical Study Protocol Number: NAV3-30

Cy3 cyanine dyes fluoresce orange (~550 nm excitation, ~570 nm

emission)

$$\begin{array}{c|c} & 1 & 3 \\ & & 1 \\ \hline & 1 \\ & & R \\ & & Cy3 \end{array}$$

DAMPs Damage-associated molecular patterns

DICOM Digital Imaging Communications in Medicine

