5.2 Investigational Product Dosage and Administration

[figure not shown]
On Day 0, subjects will receive an on label 8.0 mCi dose of unfiltered Tc 99m sulfur colloid via IV administration. On Day 3, subjects will receive 200 μg tilmanocept via IV administration at the specified radiolabeled dose of Tc 99m. A single syringe will be used for each product and injected as a slow push into the IV. At the completion of each injection, a 10 cc sterile normal saline flush will be administered. The preferred site of IV placement will be the left or right antecubital vein. The final administered tilmanocept dose will be \pm 20% of the mass dose and radiolabel mCi dose assignment.

The first two enrolled subjects will be NASH subjects who will receive an 8.0 mCi radiolabel dose of Tc 99m tilmanocept. A review meeting will be held following completion of the first two subjects to evaluate tilmanocept safety and dose performance.

At the review (as diagrammed below):

- 1. If it is determined that a lower radiolabel dose of tilmanocept may produce images of better quality, three additional NASH subjects and three HCs will be injected and imaged with 200 µg of 2.5 mCi Tc 99m tilmanocept. After these six subjects have completed the trial, no additional subjects will be enrolled.
- 2. If the review shows no safety signals and acceptable quality of imaging, one additional NASH subject as well as three HCs will be injected and imaged with 200 μg of 8.0 mCi Tc 99m tilmanocept. Once a total of three NASH subjects and three HCs have completed the trial, a second review meeting will be held to compare results from NASH subjects to those of the HCs. If it is determined at the second review meeting that a lower radiolabel dose of tilmanocept may produce additional clinically meaningful results, 3 NASH subjects and 3 HCs will be dosed with 200 μg of 2.5 mCi Tc 99m tilmanocept. If it is determined that additional doses will not provide clinically meaningful results, the trial will be concluded.

Confidential Page 39 of 71

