9.5 Statistical Analyses

9.5.1 Analysis Populations

The following analysis population will be defined for the study:

- Intent-to-Diagnose (ITD) Population Subjects who are enrolled in the study, administered Tc 99m tilmanocept and unfiltered Tc 99m sulfur colloid, and are imaged will be included in the ITD analysis population.
- Safety Population All patients who are enrolled and administered Tc 99m tilmanocept and unfiltered Tc 99m sulfur colloid in the study will be included in the safety population.

All safety data analyses will be conducted on the safety population. All efficacy data analyses will be conducted on the ITD population.

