9.5.3 Analysis of Efficacy Variables

Co-location of tilmanocept and sulfur colloid intrahepatic tessellation localization (Figure 7) will be assessed through frequency tables derived by creating virtual slices of the liver.. These scans will be false-colored and overlaid, matching landmarks (e.g. large blood vessels) for image registration. The resulting voxel colors will be classified as binding tilamanocept, binding sulfur colloid, or binding both. No formal hypothesis tests are planned. Frequency tables will created for individual subjects and overall.

The voxel radiation intensities will be used to create non-parametric density estimates of ^{99m}Tc gamma radiation intensities for both Tc 99m tilmanocept and Tc 99m sulfur colloid. Density estimates will be created for both individual subjects and for NASH subjects and healthy controls pooled separately.

[figure not shown]

Figure 7. Diagrmatic representation of anticipated tessellation

Complete analyses and details will be described in the Statistical Analysis Plan (SAP) for the study.

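### If the first review moves the trial to 2.5 mCi, the pooled NASH and control tilmanocept intensities in Section 9.5.3 confound subject type with injected activity, because no dose-group split or activity scaling is stated

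*Combined protocol and SAP*

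**What the plan says.** **Dosing path.** Section 5.2 states: "The first two enrolled subjects will be NASH subjects who will receive an 8.0 mCi radiolabel dose of Tc 99m tilmanocept". A review follows. Under its first outcome, three more NASH subjects and three controls receive 2.5 mCi, and "After these six subjects have completed the trial, no additional subjects will be enrolled". Under its second outcome, one more NASH subject and three controls receive 8.0 mCi, possibly followed by three of each at 2.5 mCi. The administered tilmanocept dose may vary by plus or minus "20% of the mass dose and radiolabel mCi dose assignment".

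**Analysis set.** Section 9.5.1 puts into the ITD set every enrolled subject who is "administered Tc 99m tilmanocept and unfiltered Tc 99m sulfur colloid, and are imaged will be included in the ITD analysis population". Both 8.0 mCi NASH subjects therefore stay in the efficacy analysis under either outcome.

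**Intensity analysis.** Section 9.5.3 forms non-parametric densities from voxel radiation intensities: "Density estimates will be created for both individual subjects and for NASH subjects and healthy controls pooled separately". The section plans no formal hypothesis test and ends: "Complete analyses and details will be described in the Statistical Analysis Plan (SAP) for the study". That SAP text is not in the supplied file.

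**Where dose group does appear.** The synopsis (Data Analyses) says: "Per subject localization rates and percentage will be calculated by time point, by subject type, Tc 99m tilmanocept dose group (if applicable), and overall". Its next paragraph gives descriptive statistics for localization intensities by time point, without a dose group, and adds: "All results will be compared to statistics computed on the control group at each time point". Sections 9.5.2 (baseline) and 9.5.4 (safety) both summarize by dose group.

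**Acquisition.** Section 8.2 anticipates 25-30 minutes per scan and sets a count target for the planar scan only. The only correction it names for the SPECT reconstruction is attenuation correction.

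**The concern.** Dose group is named for baseline, safety and localization rates. It is missing from the two outputs in which injected activity acts directly on the measured quantity: the intensity summaries and the pooled densities. Under the first review outcome no control ever receives 8.0 mCi, while two of the five NASH subjects do. Following the stated pooling rule then compares groups with different activity mixes.

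The comparison of intensity and tessellation in NASH and control livers serves the secondary objectives. Section 1.1 predicts that the degree and distribution of tilmanocept localization will differ in NASH livers, and the abbreviations list defines tessellation as differential localization or heterogeneity of signal. A pooled NASH density that is shifted upward and spread out only because two subjects received 3.2 times the activity (8.0/2.5) could be read as the predicted finding.

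**Working it through.** There is no stated figure to reproduce for this comparison. Section 9.4 gives N=12 without a variance, effect size or power.

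**Head count by branch (Section 5.2)**

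| Branch | NASH | Controls | Total |
|---|---|---|---|
| Outcome 1 | 2 at 8.0 + 3 at 2.5 mCi | 3 at 2.5 mCi | 8 |
| Outcome 2, stop | 3 at 8.0 | 3 at 8.0 | 6 |
| Outcome 2, extended | 3 at 8.0 + 3 at 2.5 | 3 at 8.0 + 3 at 2.5 | 12 |

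Only outcome 1 has unequal activity mixes.

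**Assumptions (not in the documents).** SPECT intensity is proportional to activity; scan time and liver voxel numbers are equal across subjects; the biology is identical in both groups; voxel intensities within a liver are lognormal with CV 10-80%.

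**Mean ratio, outcome 1**
- NASH: (2×8.0 + 3×2.5)/5 = 23.5/5 = 4.70
- Controls: 2.50
- Ratio: 4.70/2.50 = **1.88**, whatever the voxel CV
- With each dose drawn uniformly within ±20% of assignment (200,000 draws), the 95% range is 1.58-2.24.

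**Median ratio, outcome 1.** Solve 0.4·F(x; 8.0) + 0.6·F(x; 2.5) = 0.5 and divide by the control median, 2.5/√(1+CV²).
- CV 10%: the 8.0 mCi voxels lie almost wholly above the others, so the solution is where 0.6·F(x; 2.5) = 0.5. That gives x = 2.74; control median 2.49; ratio **1.10**.
- CV 80%: x = 3.02, since 0.4×0.151 + 0.6×0.733 = 0.500; control median 2.5/√1.64 = 1.95; ratio **1.55**.
- Between these: 1.33 at CV 30% and 1.49 at CV 50%. Below them: 1.05 at CV 5%.

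**Spread, outcome 1**
- Between-activity variance in the NASH pool: 0.4×(8.0−4.7)² + 0.6×(2.5−4.7)² = 4.356 + 2.904 = 7.26
- As a CV: √7.26/4.70 = 0.573
- Pooled voxel CV: √[(1+CV²)(1+0.573²) − 1], which is 58% when the control CV is 10% and 109% when it is 80%

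**Sensitivity to the assumptions**

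| Change | Mean ratio | Median ratio |
|---|---|---|
| 8.0 mCi intensities 25% below proportional | (16×0.75+7.5)/12.5 = 1.56 | 1.10-1.40 |
| 8.0 mCi intensities 50% below proportional | (16×0.5+7.5)/12.5 = 1.24 | 1.10-1.20 |
| 25 min scans at 8.0 mCi, 30 min at 2.5 mCi | (16×25/30+7.5)/12.5 = 1.67 | 1.10-1.46 |
| 8.0 mCi voxel share 30% instead of 40% | (0.30×8.0+0.70×2.5)/2.5 = 1.66 | 1.06-1.32 (CV 10-60%) |
| 8.0 mCi voxel share 45% | (0.45×8.0+0.55×2.5)/2.5 = 1.99 | 1.14-1.64 (CV 10-60%) |

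**After a dose-group split.** Three NASH subjects and three controls at 2.5 mCi give a nominal ratio of 2.5/2.5 = 1.00. With independent uniform ±20% doses, the 95% range of the mean ratio is 0.83-1.20. Dividing by the measured activity removes that part as well.

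**The case against.** The strongest reply is that Section 9.5.3 defers its details to an SAP, and that strata and intensity units are what an SAP normally settles. The protocol splits by dose group elsewhere, so the intent may already be there. This stands as a limit on the claim: the supplied text does not show that the final analysis will be unstratified. It does not remove the point, because the pooling rule that is written down, if followed, produces the confounding.

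Proportionality is also weakest where it matters. Outcome 1 is chosen when a lower activity is thought likely to improve image quality, so the 8.0 mCi images may not scale linearly. This stands too. A 50% shortfall reduces the mean ratio to 1.24 and the median ratio to about 1.10-1.20, but the direction does not change.

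The consequences are limited as well. The outputs are descriptive, and the required per-subject densities would show a roughly threefold offset in two of eight subjects. Within-subject relative heterogeneity does not depend on activity.

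A reader might go further and infer that the tessellation finding itself would be an artefact, that the fault runs through the whole trial, or that raw tilmanocept-to-colloid comparisons are off by 2.5/8.0 = 0.31. The documents do not support these readings. Relative heterogeneity within a liver is unaffected, the imbalance arises in one branch only, and Section 9.5.3 describes separate densities and a voxel classification, not a ratio of raw intensities.

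**Conclusion.** The point holds for the pooled tilmanocept intensity outputs under review outcome 1. As written, they confound subject type with injected activity. With no biological difference, the NASH/control mean ratio would be 1.88 if intensity is proportional to activity and scan time and voxel numbers are equal.

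The median range of about 1.1 to 1.55 is illustrative. It rests on an assumed voxel CV that the documents do not give, and should not be read as a property of the trial. The upward shift and the wider NASH density are firmer than any single figure.

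Outcome 2 is balanced between groups, with or without the extension. Sulfur colloid is 8.0 mCi for everyone. The primary safety endpoint is not affected. It is a defect in a descriptive secondary comparison, worth correcting before the data are summarized.

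**What to change.** 1. In Section 9.5.3, state that densities are shown for each subject and 'pooled by subject type within Tc 99m tilmanocept dose group'.
2. In the synopsis, add 'by subject type and Tc 99m tilmanocept dose group (if applicable)' to the intensity summaries, and make the comparison with controls within dose group.
3. State that under outcome 1 the NASH-control comparison uses the three NASH subjects and three controls at the same activity, with the two 8.0 mCi NASH subjects shown separately.
4. For any display pooled across doses, first divide SPECT intensities by the decay-corrected administered activity and by acquisition time.
5. Carry the same rules into the SAP, or confirm that it already contains them.

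The cost is a few lines of text, one scaling step, and a record of measured activity, injection and scan times and scan duration. No scans or subjects are added and dosing is unchanged. The drawback is that each displayed group has two or three subjects, and the two 8.0 mCi NASH subjects have no control at that activity.

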9.5.4 Analysis of Safety Variables

The number and percentage of subjects with any noxious pharmacologic activity or ADRs will be tabulated by dose group and overall.

All AEs will be observed for each subject from the time of signing of informed consent until exit from the study. A treatment emergent AE is defined as an AE whose start date is on or after the procedure date. If the procedure date and/or the AE start date are missing, the AE will be considered treatment emergent.

Prior to analysis, all AEs will be coded using the MedDRA coding dictionary. Based on these coded terms, treatment emergent AEs will be summarized by dose group and overall as follows:

- by system organ class and preferred terms
- by system organ class and preferred terms and relation to study drug
- by system organ class and preferred terms and severity

Observed and change from baseline vital sign parameters, ECG parameters and hematology, clinical chemistry and urinalysis parameters will be summarized using descriptive statistics (mean, median, standard deviation, minimum, maximum and range) at each time point by dose group and overall.

Other safety analyses will be described in the SAP for the study.

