4 STUDY POPULATION

4.1 Eligibility

Subjects who fulfill all respective inclusion and none of the respective exclusion criteria will be eligible for enrollment into the study. All inclusion/exclusion criteria must be verified before a subject may be considered eligible for administration of unfiltered Tc 99m sulfur colloid and imaging (Day 0 procedures). A subject will be considered enrolled in the study on the morning of study Day 0 when they arrive at the study site and receive Tc 99m sulfur colloid via IV administration. Written and dated (with time noted) informed consent will be obtained from all subjects. A subject who withdraws consent prior to arrival at the study site on Day 0 will be considered a screen failure.

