7.2.2.2 Administration of Unfiltered Tc 99m Sulfur Colloid

IV administration of unfiltered Tc 99m sulfur colloid will be at study time Day 0 Time 00:00. The preferred site of IV placement will be the left or right antecubital vein.

All subjects will receive an on label 8.0 mCi dose of unfiltered Tc 99m sulfur colloid. The filled syringe will be connected to the IV for a slow push injection. At the completion of the injection, a 10 cc sterile normal saline flush will be administered.

The IV administration will be performed in the nuclear medicine department by an onsite Certified Nuclear Medicine Technologist or Nuclear Medicine Physician. Subjects will be continuously monitored for AEs.

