7.2.3.2 Administration of Tc 99m Tilmanocept

IV administration of Tc 99m tilmanocept will be at study time Day 3 Time 00:00. The preferred site of IV placement will be the left or right antecubital vein.

All subjects will receive an open label 200 µg dose of Tc 99m tilmanocept at the specified radiolabel dose. The filled syringe will be connected to the IV for a slow push injection. At the completion of the injection, a 10 cc sterile normal saline flush will be administered.

The IV administration will be performed in the nuclear medicine department by an onsite Certified Nuclear Medicine Technologist or Nuclear Medicine Physician. Subjects will be continuously monitored for AEs.

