7.2.4 Safety Follow Up Telephone Call (Day 8 ± 3)

A safety follow-up telephone call will be performed 5 ± 3 days after administration of Tc 99m tilmanocept (Day 8 ± 3):

- o Concomitant medication review
- Assessment and review of AEs

Confidential Page 46 of 71

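### Treatment emergence rests on one undefined, date-only procedure date although every subject has two injections, and a subject given only sulfur colloid falls out of every safety table

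*Combined protocol and SAP*

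**What the plan says.** **Emergence.** Section 9.5.4 gives the rule: "A treatment emergent AE is defined as an AE whose start date is on or after the procedure date". It adds a default: "If the procedure date and/or the AE start date are missing, the AE will be considered treatment emergent". On reporting it says that "treatment emergent AEs will be summarized by dose group and overall as follows", with breakdowns by coded term, by relation to study drug and by severity. Dose group here can only be the tilmanocept radiolabel group. The Synopsis says that the reaction counts "will be tabulated by subject type, Tc 99m tilmanocept dose group (if applicable), and overall", and Section 5.3 gives everyone the same 8.0 mCi of sulfur colloid.

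**Two injections.** Section 7.2.2.2: "IV administration of unfiltered Tc 99m sulfur colloid will be at study time Day 0 Time 00:00". Section 7.2.3.2: "IV administration of Tc 99m tilmanocept will be at study time Day 3 Time 00:00". AEs are assessed before the injection on both days (7.2.2.1, 7.2.3.1), and 8.4.1.3 asks for the time of onset as well as the date. Follow-up ends with a call: "A safety follow-up telephone call will be performed 5 ± 3 days after administration of Tc 99m tilmanocept".

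**Safety population.** Under Section 4.1 a subject counts as enrolled on the morning of Day 0 "when they arrive at the study site and receive Tc 99m sulfur colloid via IV administration". Section 9.5.1 then admits only enrolled subjects who were given both products, and runs every safety analysis on that set. Section 4.4 replaces subjects who did not get both.

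**The concern.** Safety is the primary objective, and the AE tables are a large part of the evidence on it. A single anchor cannot serve two injections three days apart. Two analysts who follow 9.5.4 faithfully can build different tables from the same data, and neither table is what a reader would expect. One reports events that tilmanocept cannot have caused under a tilmanocept dose. The other drops the comparator's events.

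The population rule adds a gap. Section 4.3 lists a serious or intolerable AE among the reasons for withdrawing a subject. The subject who stops after sulfur colloid may therefore be the one who reacted to it, and that subject is removed from all safety summaries.

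**Working it through.** **1. The plan's own figures.** Day -45 to Day 11, counted as inclusive dates, is 11 - (-45) + 1 = 57, which matches the stated study duration. The dosing scheme in 5.2 gives planned totals of 2 + 1 + 3 = 6 (stop at the second review), 2 + 3 + 3 = 8 (first option) and 2 + 1 + 3 + 3 + 3 = 12 (maximum). The last matches the N of 12 in 9.4.

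**2. Where an event goes under each reading of 9.5.4.**

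| Onset | Procedure date = Day 0 | Procedure date = Day 3 |
|---|---|---|
| Day 0, before sulfur colloid | Emergent, under a tilmanocept dose | Not emergent |
| After sulfur colloid, through Day 2 | Emergent, under a tilmanocept dose | In no emergent table |
| Day 3, before tilmanocept | Emergent, under a tilmanocept dose | Emergent, under a tilmanocept dose |
| After tilmanocept | Emergent | Emergent |
| Any time, subject given sulfur colloid only | In no safety table | In no safety table |

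Only the fourth row is handled as intended under both readings. The third row is misplaced under both because the rule compares dates and ignores time. The missing-date default inherits the problem: it does not say after which injection an undated event is taken to have emerged.

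**3. Size of the disputed window.** Inputs: injections on Days 0 and 3; call 5 ± 3 days after tilmanocept, so Day 5, 8 or 11. The disputed dates are Days 0, 1 and 2.

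| Call | Dates from Day 0 | Dates from Day 3 | Disputed share of Day 0 window |
|---|---|---|---|
| Day 5 | 6 | 3 | 3/6 = 50% |
| Day 8 | 9 | 6 | 3/9 = 33% |
| Day 11 | 12 | 9 | 3/12 = 25% |

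Counted as elapsed days instead, the shares are 3/5 = 60%, 3/8 = 37.5% and 3/11 = 27%. The shift is three days under either convention. Inclusive dates suit a date-only rule.

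**4. Scale in the AE tables.** A subject whose only event starts on Days 0 to 2 moves the overall emergent-AE percentage by 1/n: 1/6 = 16.7, 1/8 = 12.5 or 1/12 = 8.3 points at the planned totals. Under the first option in 5.2 the 8.0 mCi group has two planned subjects, so one subject is 1/2 = 50 points there. Actual denominators can be larger, because a subject given both products but not imaged is replaced and still stays in the safety population.

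**5. Population rule, by illustration.** Assume one subject has an AE after sulfur colloid, never receives tilmanocept and is replaced, and 12 subjects given both products have no AE. The current rule reports 0/12 (exact 95% interval 0 to 26.5%). A set defined by either product reports 1/13 = 7.7% (0.2% to 36.0%).

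**6. Primary endpoint.** Section 9.2 requires the reaction to be observed after tilmanocept is given. It does not use the procedure date, so the choice of anchor does not enter. A subject never given tilmanocept cannot contribute to it either.

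**The case against.** The strongest reply is that little depends on this. The tables are descriptive, at most 12 subjects are planned, and no comparative AE test is intended. Onset time is collected, so any window can be rebuilt. A table by relation to study drug limits misreading. Observations from withdrawn subjects must be completed and reported (4.3), and SAEs must be reported and entered on the CRF (8.4.1.5), so no data are lost. Sulfur colloid is an on-label comparator whose safety is not a stated objective. A separate SAP might define the procedure date.

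Most of this limits the size of the point, and that stands. It does not repair the stated rules. Collecting and reporting data does not put them into the tables that 9.5.1 and 9.5.4 commit to. The relatedness table does not separate the products: the Synopsis lists both as study drug, while 5.1 identifies only tilmanocept as investigational product. Section 9.5.4 defers only other safety analyses to the SAP and defines emergence itself; no separate SAP text is in the combined document, so a later definition cannot be checked. Naming one anchor time would make the tables reproducible, but one of the two misplacements would remain.

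A reader might go further and infer that the primary endpoint is itself undefined, because 9.2 describes a reaction to a medicinal product without naming it, does not say that onset must follow the dose, and uses a loosely worded causality threshold. The documents do not support that. Sections 2.1, 5.1 and the opening of 9 point to tilmanocept, 9.2 sets its timing after tilmanocept, and 8.4.1.2 gives a working cut-off (definitely, probably or possibly related). What is left is a wording note.

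**Conclusion.** The point holds for the descriptive AE tables and the other safety summaries, as a cheap improvement. The emergence rule is ambiguous between two anchors three days apart, misplaces events under either, and ignores onset time. The safety population drops any subject given sulfur colloid alone. Neither defect changes the primary count.

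The disputed dates are 25% to 50% of the Day 0 window (27% to 60% in elapsed days). A reader might take that as the share of events misclassified. It is a share of time at risk only, and the documents give no AE rate for this setting. The 1/n figures show how coarse tables of this size are; any binary outcome here would behave the same way. The 1/13 illustration rests on an assumed event. The conclusion itself rests only on the wording of 4.1, 9.5.1 and 9.5.4 and on the injection schedule.

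**What to change.** - **9.5.4:** replace the procedure date with onset date and time relative to each injection. Period 1 runs from the sulfur colloid injection to just before tilmanocept; period 2 starts at the tilmanocept injection. Tabulate them separately and show relatedness for each product in both, so that a late sulfur colloid reaction is not assigned to tilmanocept by timing alone. State how the missing-date default applies to each period, including for a subject who has no tilmanocept date.
- **9.5.1:** define the safety population as subjects given either product, with the primary endpoint on the tilmanocept-dosed subset. With the planned sequence that subset equals the present safety population, so the primary denominator does not move.
- **9.2, wording note only:** say that onset follows the tilmanocept injection and that attribution is to tilmanocept, and refer to the cut-off in 8.4.1.2.

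The cost is wording in three sections and possibly one causality field per product on the AE CRF, which is not among the documents. Onset date and time are already required.
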